4. Metabolic acidosis is common in patients with CKD. As kidney function declines, the kidneys progressively lose the ability to synthesize ammonia and excrete hydrogen ions.²⁶ In general, ammonium excretion decreases in CKD stage 3b-4. Metabolic acidosis is more common in patients with decreasing kidney function and approximately 19%-37% of patients with CKD stage 3b-4 have a serum bicarbonate level <22 mEq/L.²⁷⁻³⁰ Recent studies suggest that positive acid balance is present in CKD even with low normal serum bicarbonate levels.²⁹⁻³¹ Metabolic acidosis results in unfavorable effects that can lead to adverse outcomes.

5. Metabolic acidosis results in increased production of angiotensin II (AII), aldosterone and endothelin-1 (ET-1). There are a number of humoral regulatory mechanisms that play a role in increasing urinary acidification in CKD including increased levels of AII, aldosterone and ET-1.³¹⁻³⁵ Experimental and human studies have shown that metabolic acidosis results in increased levels of these features and human studies have shown that metabolic acidosis results in increased levels of

these factors and increased expression of All-type 1 receptors which are found in numerous tissues including the blood vessels, kidney and brain.^{31-³⁶ Angiotensin II stimulates ammoniagenesis and increases distal nephron acidification.^{32,37} It also stimulates ET-1 and aldosterone.^{38,39} ET-1 increases both proximal and distal tubule acidification and indirectly increases acidification by stimulating aldosterone.³⁴ In CKD stage 3 patients, treatment with alkali therapy for 3 years resulted in reduced}

urinary angiotensinogen (an index of AII), reduced blood pressure (BP) and preserved kidney function.⁴⁰ Although all subjects were on angiotensin converting enzyme inhibition (ACEi), urinary angiotensinogen only decreased in those patients on alkali therapy, supporting an important role for dietary acid reduction in the decrease of AII. Alkali therapy has also been shown to reduce ET-1 and aldosterone levels in CKD.³¹

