Five cognitive summary scores were measured at baseline. Multivariate linear regression models were used to evaluate the cross-sectional association between serum bicarbonate and cognition. *Results:* The mean age (SD) and mean (SD) eGFR were 68 (8.5) years and 71 ml/min/1.73m², respectively. Global cognitive and executive functions were positively associated with serum bicarbonate (Table 1). These findings suggest that low bicarbonate levels may be detrimental to neuronal activity and support the need for an interventional trial examining whether correction of acidosis has a beneficial effect on cognitive function.

b) Bicarbonate administration results in improved vascular endothelial function (FMD) in patients with CKD stage 3b-4.⁴⁹ We performed a pilot, prospective, open label 14-week crossover study examining the effect of treatment of metabolic acidosis (defined by a low serum bicarbonate level of 16-22 mEq/L), with oral sodium bicarbonate therapy (dose 0.5 mEq/kg-lean body weight/day) in 20 patients with CKD stage 3b-4. The primary endpoint was change in FMD between treatment and control conditions. *Results:* The mean (SD) age and eGFR was 58.5 (12.8) years and 25.3 (8.3) ml/min/1.73m², respectively. The mean (SD) bicarbonate level increased after sodium bicarbonate therapy from 19.6 (2.9) mEq/L to 22.4 (3.0) mEq/L. BP control was similar between the two conditions. FMD significantly improved after 6 weeks of sodium bicarbonate therapy compared to control conditions (mean difference in %FMD 1.1% in the treatment arm vs. - 0.70% in the control arm, p=0.027), Figure 2. Bicarbonate therapy was well tolerated and there were no significant adverse events.

c) Feasibility of Aim 2 is demonstrated by our groups experience with cerebrovascular hemodynamics. In a small interventional trial of 8 adults over the age of 50 with baseline blood pressure >120 mmHg, 6 weeks of inspiratory muscle strength training (IMST) improved cerebrovascular reactivity compared to control.

	Δ CVR (Δ MCA _{velocity} / Δ end tidal CO2) from baseline Mean (SE)
IMST (Treatment Group) n=4	0.99 (0.31)
Control Group n=4	-0.14 (0.60)

IV. Research Methods

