 Age 50-80 years old Serum bicarbonate 16-22 mEq/L on 2 separate measurements (at least 1 day apart) CKD stage 3b or 4 at time of screening (eGFR 15-44 ml/min/1.73m²) Blood pressure <140/90 mm Hg prior to randomization Stable anti-hypertensive regimen for at least one month prior to randomization Montreal Cognitive Assessment Score > or = 24 No history of stroke No history of neurologic disease Able to provide consent 	 Significant comorbid conditions that lead the investigator to conclude that life expectancy is less than 1 year Use of chronic daily oral alkali within the last 3 months (including sodium bicarbonate, calcium carbonate or baking soda) Uncontrolled hypertension Serum potassium < 3.3 or ≥ 5.5 mEq/L at screening New York Heart Association Class 3 or 4 heart failure symptoms, known EF ≤30%, or hospital admission for heart failure within the past 3 months Factors judged to limit adherence to interventions Anticipated initiation of dialysis or kidney transplantation within 12 months Current participation in another research study Pregnancy or planning to become pregnant or currently breastfeeding Chronic use of supplemental oxygen 	
4 Study Drug Dosing The study drugs (bicarbonate and the matched placebo) will be		

4. Study Drug Dosing. The study drugs (bicarbonate and the matched placebo) will be prepared by A) Green Mountain Pharmaceutical and B) University of Colorado Research Pharmacy and will be identical in size, color, shape and taste. Each sodium bicarbonate capsule contains 7.7 mEq of bicarbonate and 178 mg of sodium. The matching placebo capsule will contain cornstarch. Green Mountain Pharmaceutical and/or University of Colorado Research Pharmacy will bottle the capsules and label the bottles with code numbers to maintain the study's double blind and Green Mountain Pharmaceutical will ship the bottles directly to the investigative site. Study drug supplied by the on-campus pharmacy will be managed and picked up directly from University of Colorado Research Pharmacy for each study participant.

. . .

a) Sodium bicarbonate: Subjects randomly assigned to sodium bicarbonate therapy will receive 0.5 mEq/kg-lean body weight (LBW)/day for the entire 12 months. Participants will take ½ the daily dose in the morning and the other ½ in the evening. The number of capsules will be rounded to the nearest whole capsule. To reduce pill burden and increase compliance the maximum number of pills per day will be six.

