Rationale for sodium bicarbonate dose: A dose of 0.5 mEq/kg-LBW/day has been shown to be safe and effective for treatment of metabolic acidosis in patients with CKD.^{49,53-54} Previous studies using this dose of sodium bicarbonate have not reported significant changes in edema, body weight or BP.^{49,53-55} In our **preliminary data**, sodium bicarbonate administration was not associated with an increase in BP or fluid gain in patients with CKD stage 3b-4.⁴⁹ Additionally, we will dose sodium bicarbonate based on LBW, not actual body weight. The volume of distribution of bicarbonate is approximately that of total body water. Total body water is dependent on lean body mass. Standard equations will be used to determine LBW.⁵⁶

b) Placebo: Subjects randomly assigned to placebo will take the same number of capsules as if they were assigned to receive 0.5 mEq/kg-LBW/day of sodium bicarbonate. Participants will take ½ the daily dose in the morning and the other ½ in the evening. The number of capsules will be rounded to the nearest whole capsule. To reduce pill burden and increase compliance the maximum number of pills per day will be six.

Rationale for placebo: A placebo group is necessary to successfully complete our aims. If a placebo group were not included both the investigators and participants would know that they are receiving sodium bicarbonate, which could influence medical management and perception of side effects in the study.

Dose Titration of Study Drug: If at month 3 the serum bicarbonate level not $\ge 23 \text{ mEq/L}$, we will increase the dose of sodium bicarbonate to 0.8 mEq/kg/LBW. This dose was recently used in a randomized trial comparing the safety and efficacy of doses of sodium bicarbonate therapy and was found to be well tolerated without any significant differences in adverse events or hospitalization compared with placebo.⁵⁷

5. Rationale for study duration. Changes in cognitive function, cerebrovascular reactivity and pulsatility can be seen within 4-6 weeks in adults 50 years and older but may require longer periods of time and published data use a period of 3 months to 1 year.⁵⁷⁻⁶¹ Hence, we are proposing a 12-month intervention.

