5. Safety monitoring: Sodium bicarbonate therapy may cause bloating, flatulence and abdominal discomfort. Although previous studies using similar doses of sodium bicarbonate have not reported significant changes in edema, body weight or BP,^{49,53-55} sodium bicarbonate may cause edema to develop or worsen thereby increasing BP. Sodium bicarbonate also has the potential for causing metabolic alkalosis and hypokalemia if it is retained rather than excreted in the urine. These expected adverse events will be monitored during the study. Serum bicarbonate may fall due to natural progression of CKD, particularly in the placebo group. Rescue therapy with open-label sodium bicarbonate will be initiated if serum bicarbonate is <16 mEq/L on 2 consecutive measurements until the serum bicarbonate is ≥ 16 mEq/L. Participants will not discontinue study medications if open-label sodium bicarbonate is prescribed. Please see the protection of human subjects section for full safety monitoring details.

Medical Supervision and Subject Surveillance. The Kidney Disease Research Center nursing staff will have the responsibility of performing blood draws from participants. The vascular technician will have the responsibility of performing the cerebrovascular function measurements under the supervision of [name] Director of the Vascular Biology Lab at the University of Colorado Anschutz Medical Campus. The research study coordinator will be responsible for performing the cognitive function tests and for collecting information about treatment adverse events. [name], the PI, will be responsible for supervision of the entire study. [name] will make final decisions regarding subject screening/enrollment and monitor/oversee clinical status and subject safety.

a) Data Safety Monitoring Plan. To ensure the safety of subjects, they will need to meet rigorous inclusion/exclusion criteria, including comprehensive health screening procedures. The participants' personal physicians will also be informed of their patients' participation in the study.

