• **Expected adverse events:** Sodium bicarbonate therapy may cause bloating, flatulence and abdominal discomfort. Although previous studies using similar doses of sodium bicarbonate have not reported significant changes in edema, body weight or BP,^{49,53-55} sodium bicarbonate may cause edema to develop or worsen thereby increasing BP. As shown in our preliminary data, sodium bicarbonate did not result in increased BP.⁴⁹ Sodium bicarbonate also has the potential for causing metabolic alkalosis and hypokalemia if it is retained rather than excreted in the urine. These expected adverse events will be monitored during the course of the study and in general, can be medically managed by

adjusting antihypertensive and/or diuretic agents, providing potassium replacement and by dietary changes. Of note, none of these adverse events were observed in our previous short-term pilot study. Patients will have safety visits and check-in calls to assess side effects and check laboratory values.

• Dose reduction and discontinuation:

- Serum bicarbonate >28 mEq/L: The intervention dose (study drug) will be reduced by 50% and diuretics will be adjusted as appropriate. The participant will return for a visit one week later to have serum chemistries rechecked. If the bicarbonate remains >28 mEq/L the intervention will be stopped and the participant will have serum bicarbonate measured weekly until it is <28 mEq/L. PI will monitor for symptoms of hypocalcemia as an increase in pH can decrease the ionized calcium concentration.^{117,118} Management of low calcium will be at the discretion of the PI based on symptoms reported by the patient.
- Systolic blood pressure ≥ 160 mmHg or diastolic blood pressure ≥ 90 mmHg: Potential reasons for uncontrolled BP, such as poor compliance or running out of medications will be evaluated and managed appropriately. If an identifiable cause is not found, the PI will increase anti-hypertensive medications and/or diuretics. The participant will return 1 week later for follow-up. If BP remains >160/90 mmHg at the second visit, medications will again be increased and the intervention dose will be reduced by 50%. The participant will return 1 week later. If BP remains unchanged at the third visit, the intervention will be stopped and medications will again be escalated. Participants will continue to have PRN visits weekly until BP is <160/90 mmHg.

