8. Power and Statistical Analysis: Briefly, in this pilot study a total of 50 patients will be enrolled and equally randomized to the two groups. The two-sample t-test is applicable to compare the change between the two groups for each cognitive function subdomain and is the basis for power analysis. This sample size was determined based on feasibility and availability, not a specified statistical power. With a two-sided type I error rate of 0.05, the study will have a power of 79% to detect an effect of 0.80 if 25 patients per group can be included in the final analysis. This power calculation applies to the secondary and other outcome variables. For Aim 1, we will assess the treatment effect on each of the six subdomains of cognitive function by a linear regression model with the measure at end of study regressed on treatment along with the baseline measure of the subdomain, sex, age, and baseline eGFR. Conclusion will be subdomain specific. For Aims 2 and 3, the linear regression model will be used to examine the treatment effect on the secondary and other outcomes. Particularly, the measure of an outcome variable at end of study will be regressed on intervention indicator and baseline measure of the outcome variable plus sex, age and baseline eGFR for adjustment purpose.

9. Potential Problems and Alternative Strategies

- Although subject recruitment and retention are always challenging, we should be able to complete the study in the proposed timeline given our groups excellent track record in recruiting participants in clinical trials.
- We should have few difficulties with the proposed experimental procedures and protocols as they are already established in the vascular laboratories at the KDRC by [name].
- We recognize that alternative approaches exist for examining the effects of alkali therapy on cognitive function in patients with CKD. For example, one alternative would be to undertake a larger study to examine structural changes with brain MRIs rather than the investigation proposed in the current application. However, our proposed study is the most cost-effective approach to obtain confirmation of the study hypotheses.

- We recognize that different dosages of sodium bicarbonate therapy can be used. However, the proposed dose in the current study has been shown to be safe and effective in treating metabolic acidosis in CKD 3-4.

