- Systolic BP is an important determinant of vacular function and cognitive impairment and could be a theoretical confounder. However, we do not expect this to be an issue as all participants must have their BP controlled prior to entering the study and all patients must be on an ACEi or ARB or spironolactone. We will adjust for BP if differences in BP control is observed between the groups.
- We acknowledge that there may be other potential mechanisms by which acid retention results in cerebral vessel dysfunction. Acidosis induces inflammation and oxidative stress and net calcium and phosphate efflux from bone. We will collect plasma and serum to store for future analyses of these other mechanisms.

G. Summarize Knowledge to be Gained:

The new knowledge generated from this proposal will facilitate planning of future clinical trials in CKD patients that will aim to reduce the burden of cognitive dysfunction.

H. References: REFERENCES CITED

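### Adjusting for BP only when the arms are seen to differ in BP control can replace the total effect of assignment with a data-triggered, mediator-adjusted estimate

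*Combined protocol and SAP*

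**What the plan says.** Section IV, item 8 (Power and Statistical Analysis) gives the Aim 1 model. The end-of-study score is "regressed on treatment along with the baseline measure of the subdomain, sex, age, and baseline eGFR". The model for Aims 2 and 3 has the same form. BP appears in neither.

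Section IV, item 9 (Potential Problems and Alternative Strategies) then describes systolic BP as a determinant of vascular function and cognition and a possible confounder. It says trouble is not expected, because BP is controlled before entry and patients take background renin-angiotensin or aldosterone blockade. It ends with the rule "We will adjust for BP if differences in BP control is observed between the groups".

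Other parts of the protocol bear on how to read that rule:

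- Table 1 requires "Blood pressure <140/90 mm Hg prior to randomization", and BP is measured at every in-person visit.
- In the preliminary crossover study (section III.b), the same term describes BP under treatment: "BP control was similar between the two conditions".
- Safety monitoring warns that "sodium bicarbonate may cause edema to develop or worsen thereby increasing BP". The background (section II.A.5) cites a 3-year alkali study in stage 3 CKD that "reduced blood pressure (BP) and preserved kidney function".
- Under Dose reduction and discontinuation, persistently high BP means that "medications will again be increased and the intervention dose will be reduced by 50" percent.
- The dose rationale reports that in the preliminary data "sodium bicarbonate administration was not associated with an increase in BP or fluid gain".

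**The concern.** Randomisation balances the arms in expectation at baseline, so BP measured afterwards cannot confound the comparison of arms as assigned. If treatment changes BP and BP affects cognition, BP lies on the causal path. Conditioning on it then removes the part of the effect that runs through BP. What remains can be read as a direct effect only if BP and cognition share no unmeasured causes. Both links of that path are in the protocol's own text: bicarbonate may move BP, and BP matters for cognition.

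The rule is also conditional. It switches the adjustment on when the arms differ, which is most likely when treatment has moved BP. It can therefore hide a benefit that works partly by lowering BP. It can also show a gain when a direct benefit is cancelled by a BP rise and the total effect is nil.

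Neither the trigger nor the standing of the adjusted model is defined, so two analysts could report different main results from the same data. The pilot is meant to inform a larger trial, and the effect carried forward should be clearly defined.

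**Working it through.** **Which BP is meant.** Every participant must be below 140/90 mmHg before randomisation, and BP is then recorded at all in-person visits. Section III.b uses the term for on-treatment BP. A difference in control that is later observed therefore points to follow-up BP. Baseline BP is not ruled out, and adjusting for it would not change what is estimated.

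**The plan's own figure.** With 25 per group, effect 0.80 (read as SD units) and two-sided alpha 0.05, the noncentrality is 0.80 × √(25/2) = 2.83 on 48 degrees of freedom. This gives power of 79.1%, matching the stated 79%.

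**What adjustment does.** Let treatment shift follow-up BP by *a* SD and let the BP-outcome slope be *b* SD per SD. The adjusted coefficient estimates

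total effect − *a* × *b*.

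For a total effect of 0, *a* = 0.5 and *b* = −0.3, this is 0 − (0.5)(−0.3) = 0.15.

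**What the conditional rule does.** Simulation with 20,000 trials per row, 25 per arm, within-arm SD of BP and outcome equal to 1, *b* = −0.3 and no baseline covariate. Follow-up BP is added when a t-test on BP gives p<0.05. The documents give no BP SD, slope or trigger, so *a*, *b* and the trigger are assumptions.

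True total effect 0, BP raised:

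| BP shift (SD) | Rule fires | Mean estimate | Type I error |
|---|---|---|---|
| 0 | 5.0% | 0.00 | 4.7% |
| 0.2 | 10.2% | 0.02 | 4.6% |
| 0.3 | 18.0% | 0.04 | 5.2% |
| 0.5 | 40.5% | 0.09 | 6.2% |
| 0.8 | 79.2% | 0.21 | 10.8% |

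At 0.5 SD the bias exceeds 0.405 × 0.15 = 0.06. In trials where the rule does not fire, the BP difference came out small by chance, so their unadjusted estimates also lean upward.

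BP lowered, direct benefit 0.30 (total = 0.30 + 0.3 × fall in BP):

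| BP fall (SD) | Total effect | Mean under rule | Power without rule | Power with rule |
|---|---|---|---|---|
| 0.2 | 0.36 | 0.34 | 24% | 22% |
| 0.3 | 0.39 | 0.35 | 27% | 23% |
| 0.5 | 0.45 | 0.36 | 35% | 23% |
| 0.8 | 0.54 | 0.33 | 47% | 20% |

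**At the plan's design effect.** In a separate run of 3,000 trials per cell, the true total effect was 0.80. A BP fall of 0.8 SD gave a mean under the rule of 0.59 with slope −0.3 and 0.45 with slope −0.5. Power was about 50% and 37%. Without BP adjustment it was about 80%.

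**Sensitivity.**

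- With a baseline covariate correlated 0.7 with the outcome, the bias is the same. Type I error at 0.5 and 0.8 SD becomes 7.7% and 17.8%.
- At a 0.5 SD rise and total effect 0, the bias is 0.03, 0.06, 0.09 and 0.15 for slopes −0.1, −0.2, −0.3 and −0.5.
- If the trigger is an observed difference above 0.25 SD, it fires in 38% of trials when treatment has no BP effect, against 5% for p<0.05. The bias with this trigger is 0.05, 0.14 and 0.24 at 0.2, 0.5 and 0.8 SD.

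**The case against.** The strongest reply is that harm needs two things the protocol does not establish: that follow-up BP is meant, and that treatment moves it.

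- **Baseline reading.** The confounder worry is answered by pointing to BP control before entry, which fits baseline BP too. This stands as a possibility. Even then, choosing a covariate by observed imbalance makes the model data-dependent.
- **Evidence for a BP effect.** The dose rationale says earlier studies at 0.5 mEq/kg-LBW/day reported no significant BP change, and the preliminary study saw no rise. The reference title for the study with lower BP names fruits and vegetables or oral bicarbonate, so the fall cannot be credited to bicarbonate alone. That limits how likely harm is. It does not remove it: the preliminary study covered 6 weeks of treatment, this trial runs 12 months and allows titration to 0.8 mEq/kg-LBW, and the protocol itself lists a BP rise as a risk.
- **Size.** Antihypertensive escalation should narrow any BP gap. Below about 0.3 SD the bias is 0.04 or less, against a standard error near √(2/25) = 0.28. This is correct, and the null scenarios also need a direct benefit that exactly cancels the BP harm.
- **Contingency only.** The rule sits under alternative strategies, in a pilot described as not firmly confirmatory, so it might be meant as a side analysis. The text does not say so.

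**Conclusion.** The concern holds. Followed on its natural reading, the rule replaces the total effect of assignment with an estimate adjusted for a post-randomisation variable whenever an undefined difference in BP is seen.

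The harm is conditional. There is no average bias if treatment leaves BP alone, and none if baseline BP is meant. Under the assumed slope of −0.3 and a p<0.05 trigger, harm is small for BP shifts up to about 0.3 SD and material from about 0.5 SD. These figures show direction and range; they do not predict what this trial will find. The missing trigger, BP variable and status of the adjusted model are defects on any reading. The point should be corrected, with moderate confidence that it would change a reported result.

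**What to change.** Delete the conditional sentence and state that the model in section IV, item 8 is the main analysis for every outcome. If BP adjustment is wanted, name baseline systolic BP in advance as a covariate in all models, whatever is observed. Report on-study BP and antihypertensive changes by arm. Use follow-up BP only in a supplementary or mediation analysis that is labelled as such, states its assumptions and does not replace the main result.

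The cost is wording, plus one degree of freedom if baseline systolic BP is added. The change should be made before unblinding.

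A minor separate point: item 9 says all patients must be on an ACE inhibitor, ARB or spironolactone, which Table 1 does not list. Table 1 is described as giving the major criteria only, so this is not a firm contradiction, but the two should be reconciled.
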